6.6 Dose Modification and Toxicity Management

AZD0466 may be withheld and the dose reduced due to haematological or non-haematological toxicities. In general, no AZD0466 dose modification is required if a patient experiences a Grade 1 or Grade 2 AE. However, AZD0466 should be modified or discontinued when the AEs described in this section are observed whether during ramp-up or once target dose is reached. Modifications based on cardiac AEs are described in Section 6.6.5.

Acceptable dose modifications shown in Table 4 are applicable during ramp-up and once target dose is reached. A maximum of 3 dose modifications are acceptable, except for CTCAE Grade 3 or 4 haemorrhage and any intracranial haemorrhage or haematoma, of which only one event is allowed. Also see Table 5, Table 6, Table 7, and Table 8.

Table 4 Dose Reduction Modifications

Cohort level	AZD0466 dose	Dose reductions		
		1 lower dose	2 lower doses	3 lower doses
DL-1	37.5 mg	--	--	--
	75 mg	37.5 mg	--	--
	150 mg	75 mg	37.5 mg	--
DL1	75 mg	37.5 mg	--	--
	150 mg	75 mg	37.5 mg	--
	300 mg	150 mg	75 mg	37.5 mg
DL2	150 mg	75 mg	37.5 mg	--
	300 mg	150 mg	75 mg	37.5 mg
	600mg	300 mg	150 mg	75 mg
DL3	300 mg	150 mg	75 mg	37.5 mg
	600 mg	300 mg	150 mg	75 mg
	1200 mg	600 mg	300 mg	150 mg
DL4	600 mg	300 mg	150 mg	75 mg
	1200 mg	600 mg	300 mg	150 mg
	2400 mg	1200 mg	600 mg	300 mg
DL5 ^a	1200 mg	600 mg	300 mg	150 mg
	2400 mg	1200 mg	600 mg	300 mg
	3600 mg	2400 mg	1200 mg	600 mg
DL6 ^a	2400 mg	1200 mg	600 mg	300 mg
	3600 mg	2400 mg	1200 mg	600 mg
	5400 mg	3600 mg	2400 mg	1200 mg
DL6 – alternative ramp-up ^b	1400 mg	600 mg	300 mg	150 mg
	2800 mg	1200 mg	600 mg	300 mg
	5400 mg	3600 mg	2400 mg	1200 mg

^a AZD0466 doses shown are illustrative. Actual doses will not exceed a 2-fold increase of a dose declared tolerable by the SRC, or the maximum feasible dose as specified in Section 11.4.7.5.

^b SRC to determine ramp-up as well as target dose.

DL, dose level; SRC, Safety Review Committee

While on study, patients diagnosed with COVID-19 and are thought to be receiving clinical benefit as deemed by the investigator may continue to receive AZD0466; however, must pause treatment if they meet pause or discontinuation criteria for dose modifications based on haematological parameters (Section 6.6.1, neutropenia), or CTCAE Grade 2 or higher non-haematological toxicities (Section 6.6.3), which would include pneumonia or other infectious complications.

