6.6.1 Dose Modifications Based on Haematological Parameters

Myelosuppression and cytopenias are expected outcomes of leukaemia treatment, hence the aim of these dose modification guidelines is to prevent cumulative bone marrow suppression. Dose modifications for haematological changes are not allowed in the first 35 days after starting AZD0466 during Cycle 1 but supportive care should be provided as clinically indicated.

If a patient experiences a clinically significant and/or **unacceptable haematological toxicity** (including a DLT) considered by the Investigator to be related to study treatment and not attributable to the disease (or to disease-related processes) under investigation, dosing in subsequent cycles will be withheld and may subsequently be restarted at **one lower dose** (equivalent to one dose reduction; [Figure 3](#)) and supportive therapy ([Appendix F](#)) administered as required. Recommended dose modifications for haematological toxicities associated with AZD0466 observed in patients with haematological malignancies are shown in [Table 5](#).

Table 5 Recommended Dose Modifications for Haematological Toxicities

Toxicity Grade	Occurrence	Action
Grade 4 neutropenia, with or without fever or infection	Occurrence prior to achieving remission	Administer prophylactic or treatment anti-infectives and growth factor support as clinically indicated. In most instances, AZD0466 should not be interrupted due to neutropenias prior to achieving remission; however, Investigator judgment may be applied to determine the aetiology of neutropenias.
	Occurrences after achieving remission and lasting at least 7 days	Withhold AZD0466 until infection is resolved, and antibiotics no longer required (except prophylactic) and ANC $\geq 0.5 \times 10^9/L$. ^a Dosing should be discussed with Medical Monitor.
Presence of significant bleeding events with or without thrombocytopenia, such as: 
• Grade 3 or 4 haemorrhage• Any grade serious haemorrhage event• Any grade intracranial haemorrhage or haematoma	Any	Withhold AZD0466 Maintain platelets at $\geq 50 \times 10^9/L$ until resolution of bleeding. Following discussion with Medical Monitor, if evidence of clinical benefit, may consider re-challenge at 2 dose levels below current dose.

Table 5 Recommended Dose Modifications for Haematological Toxicities

Toxicity Grade	Occurrence	Action

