For any other bleeding events eg, petechiae, purpura, bleeding gums, epistaxis, etc	Any	Monitor platelets and action as above if thrombocytopenia \geq Grade 3

^a Recovery of ANC to $\geq 0.5 \times 10^9/L$ only applicable for patients with ANC $\geq 0.5 \times 10^9/L$ at baseline/screening. For other patients discuss with Medical Monitor.

ANC, absolute neutrophil count.

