	Second and subsequent occurrences	
 Withhold AZD0466 and provide supportive therapy as per institutional guidelines. Discontinue if at ramp-up. If at target and resolution occurs in \leq 7 days: restart AZD0466 at one lower dose after discussion with Medical Monitor. If no resolution in \leq 7 days, withhold AZD0466 for up to a total of 21 days. If resolution to CTCAE \leq Grade 1 occurs within 21 days, discuss with Investigator and Medical Monitor to further dose reduce by one dose level from previous dose, and to continue treatment if the patient is deriving clinical benefit. Discontinue AZD0466 if no resolution to CTCAE Grade \leq 1 in \leq 21 days.
CTCAE Grade 4 non-haematological toxicities	Any	
 Discontinue AZD0466.

CTCAE, Common Terminology Criteria for Adverse Events (Version 5)

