For patients with normal baseline liver function: ALT and/or AST > 8 × ULN and ≤ 20 × ULN without concomitant elevation in bilirubin, which return to baseline or Grade 1 levels within 14 days OR For patients with abnormal baseline liver function: ALT and/or AST > 8 × baseline and ≤ 20 × baseline or ALT and/or AST > 10 × ULN and ≤ 20 × ULN, (whichever is lower in x ULN), without concomitant elevation in bilirubin, which return to baseline or Grade 1 levels within 14 days	First occurrence	
 Withhold AZD0466 until values return to CTCAE Grade ≤ 1 or baseline. Consider to discontinue if at ramp-up. If at target dose: Restart AZD0466 at one lower dose than the current dose.
	Second occurrence	
 Withhold AZD0466 until values return to CTCAE Grade ≤ 1 or baseline. Discontinue if at ramp-up and not previously stopped. If at target dose: Restart AZD0466 at one lower dose than the current dose and consider Q2W dosing schedule.
	Third occurrence	
 Withhold AZD0466 until values return to CTCAE Grade ≤ 1 or baseline. Restart AZD0466 at 2 lower dose levels than current dose and resume on a Q2W schedule, if all values resolve to baseline or CTCAE Grade ≤ 1 within 14 days and there is clear evidence of clinical benefit. Discontinue AZD0466 if the above criteria are not met.

Table 8 Dose Modification for Hepatotoxicity

Event	Occurrence	Action with AZD0466
For patients with normal baseline liver function: ALT and/or AST $\geq 3 \times$ ULN with concomitant elevation in bilirubin $\geq 2 \times$ ULN OR For patients with abnormal baseline liver function: ALT and/or AST $\geq 3 \times$ baseline with concomitant elevation in bilirubin $\geq 2 \times$ baseline	Any occurrence	
 Discontinue AZD0466, refer to Appendix E for process to follow in order to identify and appropriately report episodes of potential Hy's Law.
ALT and/or AST $> 20 \times$ ULN	Any occurrence	
 Discontinue AZD0466.

ALT, alanine aminotransferase; AST, aspartate aminotransferase; CTCAE, common terminology criteria for adverse events; ULN, upper limit of normal; Q2W, every 14 days

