Severe (≥ 7.0 mmol/L) or symptomatic	As above, plus Calcium gluconate ^a 100 to 200 mg/kg by slow IV infusion if concurrent ECG changes (including life-threatening arrhythmias) Regular IV insulin and dextrose, monitor blood glucose closely Consider sodium bicarbonate ^a if patient is acidotic Consider albuterol (to be avoided in patients with acute coronary disease) Dialysis may be required
Renal dysfunction (uraemia)	Fluid and electrolyte management Uric acid and phosphate management Adjust doses of renally excreted medication Dialysis or haemofiltration may be required

^a Sodium bicarbonate and calcium gluconate should not be administered through the same line.

Recommended management adapted from [University of Texas MD Anderson Cancer Center 2018](#), and [Coiffier et al 2008](#). ECG, electrocardiogram; IV, intravenous.

Laboratory parameters indicating TLS (including blood urea nitrogen, creatinine, phosphate/phosphorus, uric acid, calcium, potassium, and lactate dehydrogenase [LDH]) will be evaluated. Fluid balance must be monitored per institutional standards. If more aggressive hydration management is indicated, patient hospitalisation will be considered at Investigator discretion. Allopurinol prophylaxis should be considered based on institutional guidelines.

F 1.4 Reporting Adverse Events of TLS

The Investigator will report TLS as an adverse event or serious adverse event of "laboratory

"TLS" or "clinical TLS" according to the classification of TLS in Appendix [G 1](#). For the purposes of adverse event reporting, a CTCAE grade for TLS should also be recorded, as follows:

- CTCAE Grade 3: TLS present
- CTCAE Grade 4: TLS with life-threatening consequences; urgent intervention indicated
- CTCAE Grade 5: Death

TLS will also be graded according to Cairo-Bishop criteria for the purposes of dose-limiting toxicity assessment and summary of adverse events of special interest (Appendix [G 2](#); [Cairo and Bishop 2004](#)).

F 2 Guidance for Management of haematological changes

F 2.1 Thrombocytopenia and Haemorrhage

Platelet transfusions are permitted as per institutional standards. However, due to the mechanism of action of AZD0466, platelet transfusion may have limited efficacy within 24 to 48 hours after AZD0466 infusion.

AZD0466 should be withheld in presence of significant bleeding events with or without thrombocytopenia, such as:

- Grade 3 or 4 haemorrhage
- Any grade serious haemorrhage event

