- Any grade intracranial haemorrhage or haematoma

However, if there is evidence that the patient is experiencing clinical benefit with AZD0466, restarting at a reduced dose may be considered following discussion with the Medical Monitor. AZD0466 should be discontinued if significant bleeding reoccurs.

Anticoagulants and aspirin are not allowed during the study; other anti-aggregants may be used with caution.

F 2.2 Neutropenia and Febrile Neutropenia

The use of G-CSF (eg, filgrastim) or GM-CSF (eg, sargramostim) may be used for management of severe neutropenia or febrile neutropenia, according to institutional standards provided the patient has < 5% blasts in bone marrow and it is discussed with the Medical Monitor. The use of long-acting pegylated G-CSF (eg, pegfilgrastim) is not permitted during study treatment.

G-CSF or GM-CSF should not be administered within 72 hours prior to performing bone

marrow assessments.

F 2.3 Leucocyte Count

With the exception of hydroxyurea (AML) and high-dose steroids (ALL and leukaemia of ambiguous lineage) during screening and Cycle 1 up to 4 days (maximum dexamethasone IV 40 mg/day or equivalent), no other direct anti-leukaemia therapy is permitted once study treatment has begun. Both medications are to be used for white blood cell count control and can be started or stopped any point during this period.

F 2.4 Anaemia

Patients already receiving erythropoietin at screening may continue to receive it during study treatment, provided they have been receiving erythropoietin for > 1 month at the time study treatment is started.

Prophylaxis in Cycle 1: Prophylactic erythropoietin should not be started during Cycle 1.

Prophylaxis in cycle 2 and beyond: Prophylactic erythropoietin may be started during Cycle 2 or in subsequent cycles.

Use of the long-acting erythropoiesis-stimulating agent, darbepoetin, is not permitted during study treatment.

Blood transfusions may be administered at the discretion of the Investigator.

F 3 Guidance for Management of Fungal Infection

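### For a recurrent significant bleed outside the one-event limit in Protocol Section 6.6, Table 5 leaves re-challenge open while Appendix F 2.1 says to stop

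*Protocol*

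**What the plan says.** Three places in the Protocol govern what happens to dosing after a bleed.

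- **Section 6.6** accepts at most 3 dose modifications, "except for CTCAE Grade 3 or 4 haemorrhage and any intracranial haemorrhage or haematoma, of which only one event is allowed".
- **Section 6.6.1, Table 5** has a row for significant bleeding, with three examples: Grade 3-4, serious of any grade, and intracranial of any grade. The occurrence column applies the row to every event. The action is to withhold, support platelets until the bleeding resolves and, where there is clinical benefit and after Medical Monitor discussion, "may consider re-challenge at 2 dose levels below current dose". Recurrence is not mentioned. The next row, for lesser bleeds, reads "Monitor platelets and action as above if thrombocytopenia" of Grade 3 or higher is present.
- **Appendix F 2.1** gives the same three examples, including "Any grade serious haemorrhage event". It also permits a restart at a reduced dose after Medical Monitor discussion, and then adds: "AZD0466 should be discontinued if significant bleeding reoccurs".

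Section 2.2 describes Appendix F as additional guidance. Section 6.6.1 cites it for supportive therapy, and Section 6.6.3 cites it for TLS and specific adverse events. None of these ranks the appendix against Section 6.6 or Table 5.

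**The concern.** A site that works from Section 6.6 and Table 5 finds a restart option open at any occurrence and a one-event limit that does not cover every significant bleed. A site that reads Appendix F 2.1 finds an instruction to stop at the first recurrence. For some patients the two lead to different actions.

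The affected case is plausible. Appendix B 2 separates seriousness from severity and makes an event serious if it leads to hospitalisation or prolongs it. A Grade 2 bleed that leads to admission is therefore a serious haemorrhage without being Grade 3.

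At stake is re-exposure after a second serious bleed. Section 2.2 names thrombocytopenia as an important potential risk, and Appendix F 2.1 warns that platelet transfusion may work less well in the 24 to 48 hours after an infusion. A secondary effect is possible in the SAP: Section 4.6.2.1 counts patients who met discontinuation criteria but stayed on drug as important deviations, and the Protocol leaves unclear whether such a patient met a criterion. SAP Section 4.6.2 provides for case-by-case review, so this effect is small.

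**Working it through.** There is no planned figure to reproduce. The check compares the three texts for a **second** significant bleed.

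| Type of second bleed | Section 6.6 one-event limit | Table 5 | Appendix F 2.1 | Result |
|---|---|---|---|---|
| Grade 3-4 | Applies | Re-challenge not limited by occurrence | Discontinue | Section 6.6 and F 2.1 agree |
| Intracranial, any grade | Applies | Same | Discontinue | Section 6.6 and F 2.1 agree |
| Serious, Grade 1-2, not intracranial | Does not apply | Same | Discontinue | Section 6.6 and Table 5 leave re-challenge open; F 2.1 says stop |

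**Is the gap confined to the third row?** Not strictly. Table 5 and Appendix F 2.1 both introduce their examples with *such as*, so other bleeds could be judged significant. Any of these outside the two types named in Section 6.6 would fall into the same gap. The serious low-grade bleed is the one that the documents name.

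**Does the cap of 3 close the gap?** This depends on how it is counted.

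- By event: two re-challenges are 1 + 1 = 2 modifications, which is within 3. Re-challenge stays open.
- By dose level: two re-challenges of two levels each are 2 + 2 = 4, which exceeds 3. The second would already be barred.

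Section 6.6 words the cap as modifications and its exception as events, so counting by event is the more natural reading. Counting by level would also leave the exception little to do for bleeding, because a second two-level step would be barred anyway.

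**Is a second two-level step available in Table 4?** Yes, from dose level 2 upward.

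- From a 600 mg target: 600 to 150 to 37.5 mg.
- From a 2400 mg target: 2400 to 600 to 150 mg.
- From the 300 mg target of dose level 1: 300 to 75 mg, and then no dose two levels lower exists.

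**Does any text rank the sources?** No. The instruction after Table 6 to contact the Medical Monitor covers scenarios not described. It does not settle a difference between two that are.

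**The case against.** The strongest reply is that silence is not contradiction. Table 5 is headed as recommended and offers re-challenge only as something to consider. Appendix F 2.1 gives the same option and then completes it with a recurrence rule. Read together, the texts can all be followed by stopping. Re-challenge also needs clinical benefit and Medical Monitor discussion, and Section 7.1 lets the investigator or sponsor stop for any adverse event. All of this stands, and it is why the point is minor. It does not remove the point. Section 6.6 limits some bleeds to one event and by implication not the others, and no text tells a site to apply the stricter rule. Appendix F 2.1 also requires Medical Monitor discussion for a restart and still adds a stop, so the Protocol did not treat discussion as enough.

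Three stronger readings are tempting, and the documents do not support them.

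- *Sites are never directed to Appendix F.* Section 6.6.3, within Section 6.6, points to it for specific adverse events. The pointer is general and sits under non-haematological toxicities, but it exists.
- *Table 5 is out of line with the other dose-modification rules.* Tables 7 and 8 do handle recurrence explicitly, with entries such as "Second and subsequent occurrences" and "Any occurrence". But Section 6.6.5 (withheld cardiac findings) and Table 33 in Appendix F 1.2 (TLS) also allow a restart without a recurrence stop.
- *The case can arise only from Cycle 2.* Section 6.6.1 says "Dose modifications for haematological changes are not allowed in the first 35 days after starting AZD0466 during Cycle 1", but Section 6.6 applies its modifications during ramp-up as well, and Appendix F 2.1 withholds drug without a cycle limit. The timing is uncertain.

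**Conclusion.** The inconsistency holds for a recurrent significant bleed outside the Section 6.6 one-event limit, most clearly a serious, Grade 1-2, non-intracranial haemorrhage. It is a minor wording gap in a safety stopping rule. A reader might infer a missing safeguard or a direct contradiction, but stopping complies with every text and other checks remain in place.

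The conclusion assumes that the cap of 3 counts modification events. If it counts dose levels, Section 6.6 already bars a second two-level re-challenge, although Table 5 would still not say so. No number of affected patients can be given. SAP Section 1 records that the study was terminated, which lowers the practical urgency but leaves the Protocol text as it is.

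**What to change.** 1. **Table 5, significant-bleeding row.** Limit re-challenge to the first occurrence, keeping the present conditions (clinical benefit, Medical Monitor discussion, two dose levels lower), and add the Appendix F 2.1 instruction to discontinue on recurrence. In the next row, change the reference to the action above so that it means the action for a first occurrence. Otherwise the new stop could attach to minor bleeds such as petechiae with Grade 3 thrombocytopenia.
2. **Section 6.6, one-event limit.** Replace the two named bleed types with any significant bleeding event as described in Table 5 and Appendix F 2.1. Adding only the serious any-grade type would not fully align the texts, because both lists are open.

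The cost is Protocol wording in two places plus the conforming edit. Sample size, visits and analyses do not change. The downside is that a patient with a recurrent low-grade serious bleed loses a second re-challenge, which Appendix F 2.1 already rules out.

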6.6.2 Retreatment Criteria

Administration of AZD0466 in subsequent cycles will be guided by presence of measurable disease and adequate haematopoiesis, as described below.

Criteria for holding administration of AZD0466

The haematological criteria for withholding AZD0466 are as follows (Table 6):

- 1 **Inadequate haematopoiesis** as demonstrated by lack of peripheral blood count recovery [absolute neutrophil count (ANC) $< 0.5 \times 10^9/L$, and platelet count $< 50 \times 10^9/L$] in the absence of active bone marrow leukaemia (marrow blasts $< 5\%$).
 - Some patients with low blood counts (ANC $< 0.5 \times 10^9/L$ and platelet count $< 50 \times 10^9/L$) may have an aplastic or hypoplastic marrow ($< 10\%$ cellularity on bone marrow core biopsy). In patients with an aplastic or hypoplastic marrow and high leukaemic burden (eg, 5% cellularity and 95% leukaemic blasts), or if the Investigator determines the hypocellularity is attributable to residual leukaemia and not AZD0466, continued administration of AZD0466 may be permitted after discussion with the Medical Monitor.
 - If AZD0466 is withheld due to cytopenias and bone marrow aplasia/hypoplasia ($< 10\%$ cellularity on core bone marrow core biopsy) in the absence of leukaemia (eg, 5% leukaemic blasts), the patient should be closely monitored for blood count recovery and a repeat bone marrow assessment should be considered at weekly intervals.
- 2 **Progressive disease** (Appendix J and Appendix K): permanently discontinue AZD0466 in the absence of clinical benefit after discussion with the Medical Monitor.

Criteria for administration/continuation of AZD0466

The next cycle of AZD0466 can proceed without delay if ANC $> 0.5 \times 10^9/L$ and platelets $> 50 \times 10^9/L$ (without platelet or growth factor support). For patients without peripheral blood count recovery, the next cycle can start if there is active leukaemia with 5% or higher blasts in the bone marrow.

Table 6 Treatment Criteria Based on Bone Marrow, ANC and Transfusion Independent Platelet Count in the Absence of Peripheral Blasts

Event	ANC ($10^9/L$)	Platelets ($10^9/L$)	Bone marrow	Action
Cycle 1	> 0.5	> 50	-	
 Evaluate bone marrow disease but continue to next cycle irrespective of percentage of blasts (unless determined to have rapidly progressive disease and taken off study)
	< 0.5	< 50	< 5% blast and cellularity < 10%	
 No count recovery at day 35 hold AZD0466 wait to see if recovery at Day 42. If no recovery, repeat bone marrow at Day 42. Blasts count < 5% and no count recovery this is prolonged myelosuppression and a DLT. Discontinue AZD0466 Blasts count \geq 5% and no count recovery, either continue to Cycle 2 or discontinue due to lack of response after discussion with Medical Monitor
	< 0.5	< 50	> 5% blast	
 If significant reduction of leukaemic burden and clinical benefit as assessed by the Investigator, discuss with the Medical Monitor and may continue to Cycle 2. If lack of clinical response or benefit consider discontinuation from study.
Cycle 2 and beyond	> 0.5	> 50	< 5% blast and normal cellularity (> 10 %)	
 Continue to next cycle
			<5% blast and bone marrow hypocellular (< 10% cellularity)	
 Hold AZD0466 and monitor for count recovery and assess bone marrow weekly. Once adequate hemopoiesis met (> 20% cellularity) restart AZ0466. Consider restarting at one lower dose than the current dose.
	> 0.5	> 50	> 5% blast	
 Continue to next cycle if the patient is deriving benefit in the opinion of the Investigator
	< 0.5	< 50	Aplastic/ Hypoplastic (< 10% cellularity) and < 5% blasts	
 Hold and monitor for count recovery and assess bone marrow weekly. Once adequate hemopoiesis met (> 10% cellularity), restart AZ0466. Consider restarting at one lower dose than the current dose. If hypocellularity is due to high leukaemic burden (95% blast) or if Investigator attributes hypocellularity to residual leukaemia, consider dosing after discussion with Medical Monitor

Table 6 Treatment Criteria Based on Bone Marrow, ANC and Transfusion Independent Platelet Count in the Absence of Peripheral Blasts

Event	ANC ($10^9/L$)	Platelets ($10^9/L$)	Bone marrow	Action
	< 0.5	< 50	> 5% blast	
 Discuss with Medical Monitor consider discontinuation due to continued lack of response. Further cycles may be considered

ANC, absolute neutrophil count; DLT, dose-limiting toxicity.

Contact the Medical Monitor to discuss action with AZD0466 for any scenario not described above.

